12.8.1 Pregnancies in partners of trial subjects (only applicable to US)

In case of an SAE (with a causal relationship evaluated as possible or probable by the Investigator) in the fetus, newborn infant(s) or infant(s)/toddler(s) of a trial subject's partner, who is potentially exposed to the trial product via the trial subject, the pregnancy and the SAE should be reported on the same forms and within the same timelines as for a subject in the trial. Prior to obtaining any data on the pregnancy, "pregnant partner consent" must be completed by the male subject's partner.

12.10 Committees related to safety

12.10.1 Novo Nordisk safety committee

Novo Nordisk will constitute an internal safety committee to perform ongoing safety surveillance. The safety committee will conduct ongoing monitoring of blinded safety data. The safety committee may recommend unblinding of any data for further analysis, and in this case an independent ad hoc group will be established in order to maintain the blinding of the trial personnel.

12.10.2 The external data monitoring committee

An external data monitoring committee (DMC) is established to independently review and evaluate accumulated unblinded safety data from the trial in order to protect the safety of the subjects and to evaluate the evolving risk-benefit if required.

The DMC is composed of permanent members who are independent of Novo Nordisk and will cover relevant specialities (specialists in paediatrics and endocrinology) and they may request assistance from a number of additional ad hoc members, if needed.

The DMC is established as agreed with PDCO to review unblinded safety data after the first 12 subjects have been randomised to liraglutide and undergone dose escalation starting with a 0.6 mg dose. The DMC will also monitor safety throughout the trial on an ongoing basis, and recommend to Novo Nordisk whether to continue, modify, or terminate the trial as necessary. The composition of the DMC, objectives of the surveillance, meeting frequency and type, data to be analysed at the meetings and responsibilities with regard to information (such as meeting minutes) will be described in a DMC charter.

Novo Nordisk Global Safety must be the only point of contact between the DMC and Novo Nordisk. Other departments can participate in DMC meetings if deemed relevant by Novo Nordisk Global Safety. The DMC recommendations should be addressed directly to Novo Nordisk Global Safety and the internal Novo Nordisk safety committee. It is the responsibility of the internal Novo Nordisk safety committee to take action for subject safety based on the DMC recommendations. DMC concerns relating to trial processes will be communicated to trial management via Novo Nordisk Global Safety.

13 Case report forms

Novo Nordisk will provide a system for the electronic case report forms (eCRF) and provide paper case report forms (CRF) to site. The electronic system and support services to the system will be supplied by a vendor. The subject visit data will be captured in the eCRFs for subject Visit 1-26. The follow-up data for Visit 27-28 will be captured on paper CRFs.

The safety information forms which are used to capture information for SAEs and MESIs and the pregnancy forms (pregnancy A and pregnancy B) are paper based CRFs. The investigator must ensure that data are recorded in these forms as soon as possible and ensure that Novo Nordisk receives these forms within the required timeline (see section [12.5](#)).

Data entry for eCRFs

The investigator or delegated staff must ensure that all relevant questions are answered, and that no empty data field exists. If a test or an assessment has not been done and will not be available, or if the question is irrelevant (e.g. is not applicable), indicate this according to the data entry instructions.

Data entry for paper CRFs

Print legibly, using a ballpoint pen. Ensure that all questions are answered, and that no empty data blocks exist. Ensure that no information is recorded outside the data blocks.

If a test/assessment has not been done and will not be available, indicate this by writing “ND” (not done) in the appropriate answer field in the CRF. If the question is irrelevant (e.g. is not applicable) indicate this by writing “NA” (not applicable) in the appropriate answer field. Further guidance can be obtained from the instructions in the CRF.

Signing the CRFs

The investigator must ensure that all information derived from source documentation is consistent with the source information. By electronically signing the case book the investigator confirms, that the information in the CRFs for the trial until Visit 26 including related forms, are completed and correct. Likewise by signing the affirmation statement for each of the Visits 27 and 28 the investigator confirms that the information in the CRFs for these visits including related forms are complete and correct.

13.1 Corrections to case report forms

Correction procedure for eCRFs

Corrections to the CRF data may be made by the investigator or the investigator’s authorised staff. An audit trail will be maintained in the CRF application containing as a minimum: the old and the

new data, identification of the person entering the data, date and time of the entry and reason for the correction.

If corrections are made by the investigator's authorised staff after the date the investigator has signed the case book, the case book must be signed and dated again by the investigator.

Correction procedure for paper CRFs

Corrections to the data in CRFs may only be made by drawing a straight line through the incorrect data and then writing the correct entry next to the data that were crossed out. Each correction must be initialled, dated and explained (if necessary) by the investigator or the investigator's authorised staff. If corrections are made by the investigator's authorised staff after the date of the investigator's signature on the affirmation statement, the affirmation statement must be signed and dated again by the investigator.

Corrections necessary after the CRFs have been removed from the investigator's site must be documented on a data clarification form (DCF) or a monitor-initiated discrepancy form (MIDF). If the affirmation statement for the subject has not yet been signed, any corrections must be approved by the investigator or her/his authorised staff. If the affirmation statement for the subject has already been signed, the investigator must approve any correction.

13.2 Case report form flow

The investigator must ensure that data are recorded in the eCRF as soon as possible after the visit, preferably within 3 business days. Once data have been entered, they will be available to Novo Nordisk for data verification and validation purposes.

At the end of the trial the investigator must ensure that all remaining data have been entered into the eCRF no later than business 3 days after the last subject's last visit at the site in order to ensure the planned lock of the database.

Site specific eCRF data (in an electronic readable format) will be provided to the Investigator after the trial database is released, and access to update the trial data in electronic data capture (EDC) system has been removed. This data will be retained by the site.

When the final CTR is available the data will be archived by Novo Nordisk.

14 Monitoring procedures

During the course of the trial, the monitor will visit the trial site to ensure that the protocol is adhered to, that all issues have been recorded, to perform paper or EDC source data verification, to monitor drug accountability and collect completed CRF pages. The visit intervals will depend on the outcome of the remote monitoring of the CRFs, the trial site's recruitment rate and the compliance of the trial site to the protocol and GCP, but will not exceed 8 weeks for sites with subjects between Visits 1 and 26 (inclusive).

14.1 Source data verification

The monitor must be given direct access to source documents (original documents, data and records). Direct access includes permission to examine, analyse, verify and reproduce any record(s) and report(s) that are important to the evaluation of the trial. If the electronic medical record does not have a visible audit trail, the investigator must provide the monitor with signed and dated printouts. In addition the relevant trial site staff should be available for discussions at monitoring visits and between monitoring visits (e.g., by telephone). All data must be verifiable in source documentation other than the CRFs.

For screening failures the monitor will ensure that relevant eCRF pages and other trial related forms containing data from screening failures are completed. For screening failures the following data should be source verified: informed consent, reason for screening failure and AEs if any.

The subject diaries will be collected at each subject visit to the clinic and must be kept as source data by the investigator. The diary will be source data verified by the monitor according to guidance for reduced source data verification (SDV) in the monitoring guideline. Considering the electronic source data environment, it is accepted that the earliest practically retainable record should be considered as the location of the source data. Therefore, transcription to the diary from the blood glucose meter is considered the source document for recordings of blood glucose.

For all data recorded in the CRFs the source document must be defined in a source document agreement at each site. The list must be detailed and there should only be one source defined at any time for any data element.

The monitor must ensure that the CRFs and eCRFs are completed by site staff.

Monitors must review the medical records and other source data (e.g. the diaries) to ensure consistency and/or identify omissions compared to the CRF or eCRF. If discrepancies are found, the investigator must be questioned about these.

15 Data management

Data management is always the responsibility of Novo Nordisk. Data management may be delegated under an agreement of transfer of responsibilities to a data management unit within Novo Nordisk or an external CRO.

Appropriate measures, including encryption of data files containing person identifiable data, will be used to ensure confidentiality of subject data, when they are transmitted over open networks.

Laboratory data from central laboratories will be transferred electronically from the laboratory performing the analyses. In cases where laboratory data are transferred via non-secure electronic networks, data will be encrypted during transfer. The laboratory will provide all laboratory reports to the investigator for storage at the trial site.

The subject and any biological material obtained from the subject will be identified by subject ID and trial identification number. Appropriate measures such as encryption or leaving out certain identifiers will be enforced to protect the identity of subjects in all presentations and publications as required by local, regional and national requirements.

16 Computerised systems

Novo Nordisk will capture and process clinical data using computerised systems that are described in Novo Nordisk Standard Operating Procedures (SOPs) and IT architecture documentation. The use and control of these systems are documented.

Investigators working on the trial may use their own electronic systems to capture source data. Novo Nordisk will collect information on the practical use of these systems within the conduct of this clinical trial.

17 Statistical considerations

General considerations

Novo Nordisk will be responsible for the statistical analysis and reporting. Analysis and reporting will be based on pooled data from all sites.

The statistical analyses will be performed with a significance level of 5% (two-sided tests).

For all endpoints analysed statistically, estimated mean treatment differences will be presented together with two-sided 95% confidence intervals and p-values.

Handling of missing data

If an assessment has been made both at screening and randomisation, and if not otherwise specified, the value from the randomisation visit will be used as the baseline value. If the value measured at the randomisation visit is missing and the assessment also has been made at screening, then the screening value will be used as the baseline value.

For efficacy variables missing values will be imputed as described in section [17.3](#) and [17.4](#).

Data collected after treatment discontinuation or initiation of rescue treatment (see section [5.3.5](#)) will be considered missing in some of the efficacy analyses as described in section [17.3](#) and [17.4](#). Data collected after treatment discontinuation will be data from withdrawals collected at either Visit 17 or Visit 25 (see section [8.1.7](#)) in case the measurement is within the visit window (± 5 days) of a planned visit.

For safety variables missing values (including intermittent missing values) will be imputed using the last observation carried forward (LOCF) method on post-baseline measurements. All data for subjects receiving rescue treatment will be included.

Laboratory values below the lower limit of quantification (LLOQ) will be set to $\frac{1}{2}$ LLOQ.

17.1 Sample size calculation

The sample size has been determined in order to demonstrate superiority of liraglutide in combination with metformin with or without basal insulin treatment vs. liraglutide placebo with metformin with or without basal insulin treatment, with regards to change in HbA_{1C} from baseline after 26 weeks, using a significance level of 5% and a two-sided test.

The sample size is based on calculations for the primary endpoint alone. Assumptions for the sample size calculations are as follows:

Change in HbA_{1c}: a mean difference of 0.9% of liraglutide in combination with metformin with or without basal insulin treatment vs. liraglutide placebo with metformin with or without basal insulin treatment; Standard deviation (SD) =1.2%. The change in mean difference was chosen based on the effect of liraglutide vs. placebo observed in the adult population (LEAD 1, 2, 4 and 5 trials)¹⁵ and a paediatric PK/PD trial which included HbA_{1c} after 5 weeks of treatment as an exploratory endpoint (NN2211-1800)³⁶.

The chosen withdrawal rates (see table 17.1) are based on the withdrawal rates seen in the LEAD 2 trial¹⁵ where the withdrawal rate was approximately 40% for the placebo group and approximately 20% for the active groups. A slightly higher withdrawal rate is assumed as the trial is performed in a paediatric population. Therefore, the withdrawal rate for the active group is assumed to be 22%. The primary analysis will impute measurements for withdrawn placebo subjects based on placebo completers, and thus the sample size is not adjusted for placebo withdrawal rate.

Based on these assumptions, the sample size is set to 47 in each of the liraglutide and liraglutide placebo arms for the full analysis set (FAS) in order to achieve 80% power see [Table 17-1](#).

Assuming a screening failure rate of 65%, 269 subjects will need to be screened.

Table 17-1 Total sample size for a 1:1 randomisation

		Difference to detect in subjects with week 26 data				
Withdrawal rate		0.6%	0.7%	0.8%	0.9%	1.0%
20	Adjusted difference	0.48%	0.56%	0.64%	0.72%	0.80%
	Sample size	200	148	114	90	74
22	Adjusted difference	0.47%	0.55%	0.62%	0.70%	0.78%
	Sample size	210	154	120	94	78
25	Adjusted difference	0.45%	0.53%	0.60%	0.68%	0.75%
	Sample size	226	166	128	102	84

Power: 80%

Standard deviation of change in HbA_{1c} (%) from baseline at week 26 assumed to be 1.2%

The withdrawn subjects treated with liraglutide are assumed to have an estimated change in HbA_{1c}(%) of zero when compared to placebo.

Difference to detect: Minimum detectable difference between the changes in HbA_{1c} from baseline to week 26, between two treatment arms

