Missing week 26 data will be imputed by selecting a random observation from a normal distribution centered at the value predicted by the regression model and with variance analogous to predicting a new observation in regression analysis. For subjects on the placebo arm, the model used will be dependent on the subjects' available HbA_{1c} data throughout the trial. For example, if a subject had HbA_{1c} measurements only at baseline and week 14, then model 3 would be used. For subjects on the liraglutide arm, the measurements will be imputed using only the subjects' baseline HbA_{1c} (model 1).

The imputation procedure will be iterated 10,000 times, thus generating 10,000 complete data sets including observed and imputed values.

For each of the imputed data sets the change in HbA_{1c} from baseline to week 26 will be analysed using an ANCOVA with treatment and stratification groups (gender*age group) as categorical fixed effects and baseline HbA_{1c} as covariate. The results obtained from analysing the datasets will be combined using Rubin's rule³⁷ to draw inference.

The estimated treatment difference between liraglutide and liraglutide placebo together with two-sided 95% CI and p-value for the test of no difference in effect will be presented.

Sensitivity analyses will be performed for the primary efficacy endpoint. They will include:

- an analysis of covariance (ANCOVA) model with LOCF imputation for missing data. Data collected after treatment discontinuation or initiation of rescue medication will be handled as missing data. Effects in the model are treatment, stratification groups (gender*age group), and baseline HbA_{1c} as a covariate.
- an ANCOVA model including data after treatment discontinuation or initiation of rescue treatment and LOCF imputation for missing data. Effects in the model are treatment, stratification groups (gender*age group), and baseline HbA_{1c} as a covariate.
- multiple imputation of missing values in both treatment groups (data collected after treatment discontinuation or initiation of rescue treatment considered as missing) based on parameters estimated from the placebo group. The same model as for the primary analysis will be used.
- a RMA model using all data points for all visits, but excluding data collected after treatment discontinuation or initiation of rescue medication. Fixed effects in the

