Missing week 26 data will be imputed by selecting a random observation from a normal distribution centered at the value predicted by the regression model and with variance analogous to predicting a new observation in regression analysis. For subjects on the placebo arm, the model used will be dependent on the subjects' available HbA_{1c} data throughout the trial. For example, if a subject had HbA_{1c} measurements only at baseline and week 14, then model 3 would be used. For subjects on the liraglutide arm, the measurements will be imputed using only the subjects' baseline HbA_{1c} (model 1).

The imputation procedure will be iterated 10,000 times, thus generating 10,000 complete data sets including observed and imputed values.

For each of the imputed data sets the change in HbA_{1c} from baseline to week 26 will be analysed using an ANCOVA with treatment and stratification groups (gender*age group) as categorical fixed effects and baseline HbA_{1c} as covariate. The results obtained from analysing the datasets will be combined using Rubin's rule (1) to draw inference.

The estimated treatment difference between liraglutide and liraglutide placebo together with two-sided 95% CI and p-value for the test of no difference in effect will be presented.

Sensitivity analyses will be performed for the primary endpoint. They will include:

- 1. an analysis of covariance (ANCOVA) model with LOCF imputation for missing data. Data collected after treatment discontinuation or initiation of rescue medication will be handled as missing data. Effects in the model are treatment, stratification groups (gender*age group), and baseline HbA_{1c} as a covariate. The LOCF will be performed using data collected at time points in the treatment period (on treatment) and before initiation of rescue medication, or data at baseline if there is no data on treatment without rescue medication post baseline.
- 2. an ANCOVA model including data after treatment discontinuation or initiation of rescue treatment and LOCF imputation for missing data. Effects in the model are treatment, stratification groups (gender*age group), and baseline HbA_{1c} as a covariate. The LOCF will be performed using baseline data, if this is the only available data, and otherwise data collected at time points during the trial.

Liraglutide
Trial ID: NN2211-3659
Statistical Analysis Plan
EurdraCT No.: 2011-002605-29

Date: 25 June 2018 Version: 2.0
Status: Final
Page: 15 of 25

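### The 80% power counts every placebo week 26 value as observed, because Section 17.1 wrongly infers that imputation removes the need to allow for placebo withdrawal

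*Protocol*

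**What the plan says.** Protocol 17.1 assumes a difference of 0.9 percentage points in HbA1c, an SD of the change "from baseline at week 26 assumed to be 1.2"%, two-sided 5% significance and 80% power. From these, "the sample size is set to 47 in each of the liraglutide and liraglutide placebo arms". Table 17-1 labels its columns "Difference to detect in subjects with week 26 data" and multiplies each difference by one minus the liraglutide withdrawal rate, assumed to be 22%. The note explains the dilution: "The withdrawn subjects treated with liraglutide are assumed to have an estimated change in" HbA1c of zero relative to placebo.

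For the source of the rates, 17.1 cites an adult trial in which "the withdrawal rate was approximately 40% for the placebo group and approximately 20% for the active groups". The placebo rate then drops out of the calculation, because the plan is to "impute measurements for withdrawn placebo subjects based on placebo completers, and thus the sample size is not adjusted for placebo withdrawal rate".

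The analysis itself is in Protocol 17.3 and SAP 3.5. Missing week 26 values are "imputed by selecting a random observation from a normal distribution" centred on a prediction from placebo completers, with the variance for predicting a new observation. There are 10,000 imputed data sets, each analysed by ANCOVA with strata and baseline HbA1c. "The results obtained from analysing the datasets will be combined using" Rubin's rule. SAP 3.4 only refers back to the protocol for sample size.

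**The concern.** Missing data can reduce power in two ways: by shrinking the expected difference and by increasing the uncertainty. Section 17.1 deals with the first, and only for liraglutide. For placebo it is right that imputing from the same arm's completers does not shrink the effect. The second way remains. Random draws pooled by Rubin's rule add between-imputation variance, and this grows with the share of placebo values imputed.

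The primary test also gates three confirmatory secondary endpoints (FPG, HbA1c below 7.0%, BMI SDS). If true power were about 70%, the chance of missing the assumed effect would be about 30% instead of the 20% implied.

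**Working it through.** **1. The plan's figure.** Inputs from 17.1: difference 0.9, SD 1.2, 22% liraglutide withdrawal, 47 per arm, two-sided 5%.

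- Diluted difference: 0.9 × 0.78 = 0.702.
- SE = 1.2 × √(2/47) = 0.2475.
- Noncentral t on 92 degrees of freedom: power 80.1%.

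All 15 cells of Table 17-1 reproduce this way. The table is correct as a complete-data calculation, with all 47 placebo values observed.

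**2. Adding placebo missingness, with no covariates.** Let *p* be the fraction of placebo week 26 values missing and *n*P = 47(1 − *p*) the number observed. Keep 22% missing on liraglutide, so 47 × 0.78 = 36.66 are observed there. Assume no usable data after withdrawal.

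- Estimate: 0.78 × (liraglutide completer mean − placebo completer mean), expected value 0.702.
- Sampling variance: 0.78² × 1.44 × (1/36.66 + 1/*n*P).
- Within-imputation variance: W = (1.44 + 1.44 + 0.9² × 0.22 × 0.78)/47 = 0.0642. The last term is the mixture of completers and placebo-like dropouts on liraglutide.
- Between-imputation variance: B = 1.44 × (1 + 1/*n*P) × (0.22 + *p*)/47.
- Rubin SE = √(W + B); the 1/m term is negligible with 10,000 imputations.
- Barnard-Rubin df ≈ (93/95) × 92 × W/(W + B).
- Power ≈ Φ[(0.702 − t × Rubin SE)/sampling SD].

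At *p* = 40%, *n*P = 28.2 and B = 1.44 × 1.0355 × 0.62/47 = 0.0197. The Rubin SE is √0.0839 = 0.290, df is about 69 and t = 1.995. The sampling SD is 0.234, and power is 70.2%.

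| Placebo missing | Sampling SD | Rubin SE | Power |
|---|---|---|---|
| 0% | 0.206 | 0.267 | 79.7% |
| 22% | 0.219 | 0.279 | 74.7% |
| 40% | 0.234 | 0.290 | 70.2% |
| 44% | 0.239 | 0.292 | 69.1% |

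Simulation without covariates gives 79, 74, 69 and 68% for the same rows.

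**3. The specified ANCOVA.** Simulation with 10,000 replicates per cell and 100 imputations (Monte Carlo error at most 0.5 points), four strata (60/40 sex, 70/30 age), marginal SD of change 1.2, withdrawal at random and Model 1 imputation. The baseline-change correlations and 20% on insulin are assumptions; the documents give neither.

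| Correlation | 0% | 10% | 22% | 30% | 40% | 44% |
|---|---|---|---|---|---|---|
| 0 | 75 | 73 | 69 | 65 | 61 | 59 |
| −0.3 | 80 | 77 | 73 | 70 | 66 | 63 |
| −0.5 | 88 | 85 | 82 | 79 | 75 | 74 |
| −0.6 | 93 | 91 | 88 | 86 | 82 | 80 |
| −0.7 | 97 | 96 | 95 | 93 | 90 | 89 |

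Columns are placebo missing rates; entries are power (%). Relative to no placebo missing, the loss in these rounded figures is 2 to 7 points at 22%, 7 to 14 at 40% and 8 to 17 at 44%.

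**4. Data that reduce the loss.** Suppose 25% or 50% of withdrawn subjects have a usable week 26 value, or every placebo dropout has an interim HbA1c with residual correlation 0.8 (all assumed). The loss at 40% is then 4 to 10 points for correlations 0 to −0.6. Power is 66 to 73% at correlations 0 to −0.3, 79 to 82% at −0.5 and 85 to 88% at −0.6.

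**5. What rate is plausible.** Protocol 6.1 expects 63 completers. With 22% lost on liraglutide, 63 − 36.66 = 26.34 remain on placebo, which is 56% of 47, so 44% are lost. That count is at Visit 26 (week 53), so 44% is an upper bound for placebo withdrawal by week 26.

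**6. Type I error.** With 40% of placebo values missing and no true effect, simulated one-sided rejection is 0.7 to 0.9% against a nominal 2.5%.

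**The case against.** The strongest reply is that 17.1 discloses its simplification, that Table 17-1 is arithmetically right, and that a shortfall below 80% is not proven. Several parts of this stand:

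- The only withdrawal adjustment in 17.1 is dilution, and no dilution is needed for placebo. The sentence is right about bias in the effect and wrong only about precision.
- Withdrawal is not the same as a missing week 26 value. Rescued subjects stay in the trial (5.1), data after discontinuation and rescue are used (17.3), and a withdrawal-visit measurement counts if it falls within 5 days of the planned visit (17, handling of missing data).
- The 70% figure omits baseline adjustment, which the plan includes. A strong baseline correlation can keep power at 80% or above.
- Part of the loss comes from Rubin's SE being conservative here. The sampling SD at 40 to 44% missing (0.234 to 0.239) is still below the 0.2475 behind the plan's figure. Part of the wider SE (0.267 with no placebo missing) comes from liraglutide imputation.
- Planned last visit, 15 July 2018, less the 67-week maximum duration is 2 April 2017, one day before protocol version 7.0. On planned dates, a restated power could hardly have changed enrolment.

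None of this rescues the inference. Section 17.1 does not appeal to baseline correlation, retrieved data or interim values; it appeals to imputation. The conservatism belongs to the specified test, and so to its power. Liraglutide imputation alone leaves power at 79.7% in the no-covariate calculation, because the sampling SD falls as the SE rises. The further drop comes from the omitted placebo term.

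**Conclusion.** The point holds. The stated 80% is the power of a complete-data comparison, and the reason given for ignoring placebo withdrawal is wrong for an analysis pooled by Rubin's rule. The direction is certain: power falls as more placebo values are imputed. The size is conditional. On 17.1's own SD and difference without covariates, power drops by 5.0 points at 22% placebo missing (79.7 to 74.7%) and 9.5 points at 40% (79.7 to 70.2%).

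Whether actual power is below 80% cannot be settled from the documents. It depends on the placebo missing rate, the baseline and week 10/14 correlations and how many withdrawn subjects have usable week 26 data. This should be fixed because the stated power of the confirmatory test is unsupported; the validity of the test is not in question.

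**What to change.** In Protocol 17.1, remove the clause that infers no adjustment from imputation. Say instead that Table 17-1 treats all placebo week 26 values as observed, and that imputed placebo values pooled by Rubin's rule lower power. This keeps the disclosure and drops the faulty reason.

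Then state the assumed week 26 placebo missing rate, the assumed baseline and week 10/14 correlations, and the assumed fraction of withdrawn subjects with usable week 26 data. With those inputs, the sponsor should restate the power of 94 subjects under the specified placebo-based imputation, over a range of placebo missing rates that includes 0, 22 and 40%. Carry the same statement into SAP 3.4. The figures above show direction and size only and should not be entered as the trial's power.

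The cost is one paragraph, one simulation and possibly a less favourable stated power. It needs no extra subjects, no new data and no change to the analysis that was revised at the FDA's request.
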